Within each of the 5 study sites, we will randomize 25 (one-week blocks) to the PROCOVAXED intervention and 25 (one-week blocks) to usual care using one-week periods with blocks of concealed size to ensure equal allocation to the two intervention settings. Our randomizations will be computer-based pseudo-random sequences of 7 days periods, stratified by study center. We will develop 60 random sequences separately for each center which will be enough to last the study for up to 14 months. We will stratify sequences by study week period so that 3 centers will be in the control condition for one week and 2 centers will be in the experimental condition for one week, or vice versa. This will minimize the effect of secular trends on the comparison of the intervention. We will generate a 60-week study calendar based on this randomization scheme. To try to maintain masking of allocation, sites will not be notified of their treatment assignment for the next week no more than 3 days prior to that week.

- **Site Orientation and Training**

The Core UCSF Site will develop orientation materials to familiarize the ED Sites with the study protocol. Each site will employ one or more Clinical Research Coordinators (CRCs), who will report to the Site PI and be responsible for day-to-day study implementation. We will develop and disseminate a manual of operating procedures (MOP) with standard personnel training methods, including education kits with scripts, summary cards, and PowerPoint presentations to assist coordinators in the orientation of site clinicians and other staff to our study protocol. We will convene ZOOM conference calls to review this summary and develop plans for optimization of PROCOVAXED platforms to improve usability and workflow. We will refine procedures with updates delivered to the site PIs during weekly ZOOM conferences.

- **Study Hotline and Quality Assurance**

We will maintain a study hotline and encourage study personnel to contact the PI and Central Study Coordinator for all issues and queries. Hotline hours will be during primary study hours (weekday 8 a.m. to 5 p.m. PST).

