The two primary outcomes are the verbal acceptance (Second Survey response) of a Covid vaccine in the ED and the receipt of at least one dose of a Covid vaccine dose within 30 to 32 days after the index ED visit. Both outcomes will be compared using mixed logistic regression with a fixed effect for randomization assignment, a random slope to allow for clustering by enrolling center, and a random slope to allow for secular trends. The treatment effect will be tested by the coefficient for the fixed effect of intervention along with 95% confidence intervals

- **Sub-analyses**

Another focus of this research is on the ED Usual Source of Care group, defined on the FIRST SURVEY questions as

- An answer of “No” or “Unsure” to the question: “*Do you have a regular clinic or doctor for medical care?*”

OR,

- *If they say “Yes” to the question: “Do you have a regular clinic or doctor for medical care?”, an answer of > 2 years to the question “If YES to regular doctor, when was the last time you saw this doctor or went to this clinic?”*

We will conduct subgroup analyses of the same primary outcomes of this ED Usual Source of Care group.

We will additionally stratify outcomes by study site (representing different regions of the country and different communities), age, gender, and race/ethnicity. We will also analyze outcomes according to patient-level experience characteristics, such as having already had COVID-19.

- **Rationale for time (1 week unit) cluster and consideration of Alternative Study Designs:**

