Our primary goal with this research is to determine whether real-world implementation of PROCOVAXED as an ED-site level intervention results in greater acceptance and uptake of COVID-19 vaccines in vulnerable ED populations. Each site sees approximately 150-250 patients per day and applying or not applying the intervention (delivery of PROCOVAXED messaging) *for individual patients* in this high workflow, rapid patient turnover ED environment is simply impractical. Patient level randomization may also result in high risk of cross-contamination between intervention and control arms in terms of the messaging flyer and direct ED provider messaging platforms. Therefore, removal of the intervention from the site completely during specified time periods (1-week units) of non-intervention is the optimal approach. Although a single switch of the intervention at each site (i.e., stepped-wedge trial design) is easier to enact, changes in general population attitudes over time introduce bias that limit the validity of this trial method. We expect gradually increasing acceptance of the COVID-19 vaccine over time, which would introduce substantial bias toward the intervention. These practical and methodological benefits of the 1-week unit cluster RCT far outweigh the smaller sample size and easier analysis with an individual patient unit RCT or a stepped-wedge design.

Statistical approach: In terms of statistical approach, this is a superiority trial in which we seek to verify our central study hypothesis that provision of PROCOVAXED will

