result in greater acceptance and uptake of the COVID-19 vaccine. Following the recommendations of Hussey and Hughes, our statistical analyses of AIMS III and IV will focus on comparing the vaccine and uptake rates during the time periods when PROCOVAXED is in place (intervention) and when the system is not in place (usual care) using mixed effects logistic models.^{122,123} The outcomes of interest are the binary indicators of whether a patient will accept the COVID-19 vaccine ("Will you accept the COVID-19 vaccine if it was offered to you" – yes/no) and whether they have received a COVID-19 vaccine (uptake - yes/no) upon follow-up. Models will include a random center effect to accommodate potential within-center characteristics (e.g., case mix, demographics), as well as terms for time and intervention. Hypothesis tests will focus on the statistical significance of the intervention indicator. We will fit the mixed effects models using maximum likelihood and routines in Stata or SAS.

We will test our primary hypothesis and analyze outcomes according to the study arm (index visit in intervention month vs non-intervention month) to which patients were allocated, regardless of whether they received PROCOVAXED messaging or not - **intention to treat analysis**. We will also conduct a **per-protocol analysis**, in which we assess results that would occur if they actually did or did not receive PROCOVAXED messaging (e.g., viewed the video clip given to them) during their index visit (ascertained by direct questioning in the Outcome Survey). When compared to the primary analysis, the per-protocol analysis will allow us to dissect the reasons for success (or failure) in demonstrating improved vaccine acceptance and uptake with PROCOVAXED. For example, if we find better acceptance and uptake in the per protocol analysis and not in the intention to treat allocation analysis, we would subsequently seek ways to improve delivery of PROCOVAXED messaging. Conversely, if both analyses fail to improve acceptance, then the PROCOVAXED intervention truly fails and other efforts to improve delivery would not be indicated. In addition to the effects on *total* vaccine acceptance, we will also examine the effect of PROCOVAXED on acceptance in patient sub-groups, especially African Americans and Latinos. PROCOVAXED may work for one patient sub-group and not others - these additional analyses will guide future directions and modifications of PROCOVAXED messaging.

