vaccination in ED USCARE patients. Considering the commonality of hesitancy (non-acceptance), the high benefit of increasing acceptance and the negligible risk of the intervention (a trusted messaging program), even a small effect size of increased acceptance would be a clinically important difference. By investigator consensus and in consultation with a panel of health policy experts, we have determined that PROCOVAXED would be clinically useful if it increased acceptance by 7%. Similarly, with the same considerations of negligible risk, we have determined that PROCOVAXED would be useful with an effect size on vaccine uptake of 7%. Our sample size calculations accommodate the randomization of clusters design consisting of 1 week periods (implementation of PROCOVAXED months and non-implementation) to the intervention at each of six sites. To avoid period effects, we will assign sites using a Latin square design S2. This design is more efficient than either the randomization of site for the study period or for individual subject randomization. We base the sample size calculation on the comparison of the proportion of patients who accept the vaccine between the PROCOVAXED and usual care time periods using standard formulae for individual randomization. We have verified that these sample sizes are conservative by simulation of data using a mixed random effects model. When our protocol was originally written in February 2021, vaccines were not widely available and the degree of baseline vaccine acceptance and uptake was unknown. We therefore calculated sample sizes for a wide range of vaccine acceptance and uptake rates with a plan to measure these in the non-intervention (control) group during the first month of the trial. After the first month, we estimate that our baseline vaccine acceptance and uptake rates (without intervention) will be approximately 15%. With this baseline uptake rate of 15%, we find that at an alpha=0.05 level and a power of at least 0.9, we will need to enroll 1,290 patients (645 in each arm) in the study to detect the difference of interest (a setting in which the vaccine acceptance rate will increase by 7% in PROCOVAXED weeks).

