With this same baseline 15% rate of uptake and the same specifications for power, we will need to enroll 1,290 patients (645 in each arm) to detect a vaccine uptake difference (the primary outcome of Specific Aim IV) of 7%. Thus, our target enrollment for this implementation trial is 1290 subjects across all sites.

In terms of total projected time for enrollment, we expect a minimum enrollment of 1 subject per site per day (6 hour block) at the 5 sites, or 25 enrollees per 5 day work week. We therefore expect to attain our target enrollment of 1290 subjects in approximately 50 weeks.

- **Consents and Rationale**

Survey Consent We will obtain scripted verbal consent for the surveys in the usual manner that we have conducted other survey studies of similar design and scope - (CHR. See 2 versions of this Scripted consent for the Intervention periods and for the Non-intervention periods. (Intervention and Non-Intervention).

We will obtain written consent for follow up chart review and phone calls. See FOLLOW UP Consent.

With regards to consent for delivery of the intervention (Covid vaccine

messaging) during intervention periods, we must emphasize that messaging for vaccine hesitancy is firmly a part of standard best-practice emergency department care (messaging of this type is currently be enacted in EDs across the US). Delivery of all of the vaccine messaging platforms is therefore an accepted common best practice not requiring consent. To add an extra layer of consent could even lead to greater vaccine hesitancy. We therefore plan the following processes with verbal assent during the PROCOVAXED FIRST SURVEY in intervention months:

- Handing patients the Covid vaccine message information sheet at the end of the first survey.
- Informing the patient's provider(s) of the short scripted vaccine message to deliver to the patient sometime after the FIRST SURVEY
- At the end of the FIRST SURVEY, asking patients if they are willing to watch the vaccine messaging video(s). If the patient says Yes, then we will play the video. If the patient says no, we will not play the video.

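### Neither description of the primary model includes the randomised unit, the site-week, so standard errors for both primary outcomes may be too small; the two descriptions also differ

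*Combined protocol and SAP*

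**What the plan says.** **The randomised unit.** The Randomization section (V) states: "Within each of the 5 study sites", "we will randomize 25 (one-week blocks) to the PROCOVAXED intervention and 25 (one-week blocks) to usual care". In any week three sites are in one condition and two in the other. The Rationale part of Data Analysis (XVI) names the design: "These practical and methodological benefits of the 1-week unit cluster RCT far outweigh" the alternatives considered. Sample Size Considerations (XVIII) agrees: "Our sample size calculations accommodate the randomization of clusters design consisting of 1 week periods".

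**The model, first description.** Under Primary Analysis, both primary outcomes (acceptance at the second survey and uptake at follow-up) are analysed by mixed logistic regression with a fixed arm effect, "a random slope to allow for clustering by enrolling center, and a random slope to allow for secular trends".

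**The model, second description.** Under Statistical approach, for the same two outcomes: "Models will include a random center effect to accommodate potential within-center characteristics", together with terms for time and intervention. The form of the time terms is not given.

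**The sample size.** It was obtained "using standard formulae for individual randomization". The section adds that a mixed-model simulation showed the result to be conservative, but gives no model terms, variance components or ICC for it. Expected recruitment is "a minimum enrollment of 1 subject per site per day (6 hour block) at the 5 sites".

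**The concern.** The plan justifies itself as a cluster trial with the week as the cluster, but its analysis does not recognise that cluster. Once centre and a time trend are in the model, patients in the same randomised site-week are treated as independent. Those patients may share a coordinator who asks the questions orally, the same ED providers delivering the scripted message, and the same vaccine availability. A centre effect and a smooth trend need not absorb all of that.

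If such correlation exists, the standard error of the intervention coefficient is understated, the interval is too narrow, and the false-positive rate exceeds 5% for both primary outcomes. If it does not exist, the omission does no harm. With no ICC in the documents, neither case can be assumed.

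The two descriptions also cannot both be followed. One has a slope for centre, without saying on which variable, and the other has a centre effect. One has a random slope for time, and the other has unspecified time terms.

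**Working it through.** **Inputs from the documents.** 5 sites; 25 + 25 one-week blocks per site; 1,290 patients, 645 per arm; 15% versus 22%; alpha 0.05; power at least 0.9. Sample Size Considerations mentions six sites in one place; 5 is used here, as everywhere else.

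**Step 1: the plan's own figure.** Two-sided pooled two-proportion formula, no continuity correction:

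n = [1.960·√(2 × 0.185 × 0.815) + 1.282·√(0.15 × 0.85 + 0.22 × 0.78)]² / 0.07² = (1.0763 + 0.7009)² / 0.0049 = 644.6, so 645 per arm.

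The stated 1,290 reproduces exactly, with no design effect in it.

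**Step 2: cluster size.** 5 × 50 = 250 site-weeks; 1,290/250 = 5.16 patients each. This agrees with 25 enrollees a week over 5 sites.

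**Step 3: formula.** With equal clusters, DE = 1 + (5.16 − 1) × ICC. With an assumed cluster-size coefficient of variation (CV) of 0.5, DE = 1 + (1.25 × 5.16 − 1) × ICC. The true standard error is √DE times the one that ignores site-week. Type I error = 2 × [1 − Φ(1.96/√DE)]. Power uses 645/DE per arm. The ICCs are assumptions, on the response scale at a 15% rate.

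| ICC | DE (equal) | √DE | Type I (equal) | Type I (CV 0.5) | Power (equal) |
|---|---|---|---|---|---|
| 0 | 1.000 | 1.00 | 5.0% | 5.0% | 90.0% |
| 0.01 | 1.042 | 1.02 | 5.5% | 5.6% | 88.8% |
| 0.02 | 1.083 | 1.04 | 6.0% | 6.3% | 87.6% |
| 0.05 | 1.208 | 1.10 | 7.5% | 8.2% | 83.9% |

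**Step 4: simulation.** 6,000 null trials per ICC: 5 sites × 50 weeks, 3:2 or 2:3 weekly allocation, 25 weeks per arm per site, mean 5.16 patients per site-week. Assumed: CV 0.5, centre SD 0.3 on the logit scale, and a mild linear trend. Site-week logit SDs of 0, 0.280, 0.397 and 0.634 give ICC 0, 0.01, 0.02 and 0.05. Linear time stands in for the unspecified time terms. Type I error:

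| Model | ICC 0 | 0.01 | 0.02 | 0.05 |
|---|---|---|---|---|
| Statistical approach model (random centre, linear time, arm) | 5.1% | 5.7% | 6.7% | 7.9% |
| Fixed centre, linear time, arm, site-week random intercept | 5.0% | 5.4% | 5.7% | 5.2% |
| Fixed centre, linear time, arm, site-week cluster-robust errors | 5.9% | 5.6% | 5.9% | 5.4% |

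The Monte Carlo standard error is √(0.05 × 0.95/6,000), about 0.3 points, so the ICC 0.01 column is close to noise.

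**Step 5: a second model.** A separate simulation (2,000 trials per setting, Monte Carlo error about 0.5 points) fitted centre, centre-specific time slopes and arm, which is one reading of the Primary Analysis wording. At site-week logit variances 0, 0.033, 0.067, 0.173 and 0.366, type I error was 4.9%, 4.9%, 5.0%, 7.3% and 8.5%. The last two variances correspond to SDs of √0.173 = 0.416 and √0.366 = 0.605, close to the 0.397 and 0.634 in Step 4, and the error rates are similar. Centre-specific trends do not remove the problem.

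**Step 6: what the ICCs mean.** With an average rate of 15%, the central 95% of a site's weekly true rates runs from about 7% to 27% at ICC 0.02 and from about 4% to 35% at ICC 0.05.

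**The case against.** **Shared weekly shocks nearly cancel.** This is the strongest point, and it stands. Because each week splits the sites 3:2, a shock common to all sites contributes little: DE = 1 + (5.16/5 − 1) × ICC, or 1.002 at ICC 0.05. In simulations with a shared week effect, type I error was 5.3% to 5.5% at SD 0.397 and 5.6% to 6.0% at SD 0.634. Only week-to-week variation specific to a site does the damage. The ICCs above must be read as that component alone, which makes the upper end less likely.

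**The Primary Analysis wording might mean time nested in centre.** For weekly time that would amount to a site-week effect. The words do not say so: they list one term for centre and a separate one for secular trends. If that was the intention, the text needs to state it.

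**The comparison with the remedy is not like for like.** This is correct: the planned model has random centre and the alternative has fixed centre, so the differences in Step 4 are not purely the effect of one added term. The gains are small at ICC 0.01 and 0.02. Cluster-robust errors ran slightly above nominal even at ICC 0 (5.9%).

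**The sample-size simulation already covers this.** It cannot settle the point. It is cited for sample size rather than for the analysis standard error, and its terms are not described.

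**The wording difference may be a slip of slope for intercept.** Possibly, but as written a reader cannot tell which model is to be fitted.

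**Conclusion.** The concern holds and should be fixed. Two parts are certain from the text: the randomised unit appears in neither description of the primary model, and the descriptions differ.

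The size is conditional. With about 5 patients per site-week, type I error rises from 5% to about 6% to 7% at ICC 0.02 and to about 7.5% to 8% at ICC 0.05, counting only site-specific weekly variation. It is negligible at 0.01 and absent at 0. The ICCs, cluster-size variation, centre SD and linear trend are all assumed. The likely effect is modest, but the plan offers nothing that rules out the larger values.

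**What to change.** Replace both descriptions with one model for both primary outcomes: logistic regression with intervention, centre, explicitly stated calendar-time terms, and a random intercept for site-by-week. Standard errors clustered on site-week are an acceptable alternative, though the random intercept held the error rate slightly closer to nominal here. Delete or correct the random-slope wording under Primary Analysis, make Statistical approach match it, and report the estimated site-week variance or ICC. State the model terms and ICC used in the sample-size simulation.

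The cost is SAP wording and one model term. No extra patients or data are needed, because site and study date are already recorded. Intervals widen slightly if site-week correlation exists. Power at 1,290 would then be somewhat below 90%, as shown in the Step 3 table. That loss comes from the correlation itself; the added term only makes it visible.

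### Calendar study week is a randomisation stratum, but the primary model names no shared week effect; the harm is small if the stated 3:2 weekly split is enforced

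*Combined protocol and SAP*

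**What the plan says.** All references are to the combined protocol and SAP.

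- **Section V (Randomization), the rule.** "We will stratify sequences by study week period so that 3 centers will be in the control condition for one week" and the other 2 in the intervention condition, or the reverse. The reason given is: "This will minimize the effect of secular trends on the comparison of the intervention".
- **Section V, making the lists.** The same paragraph says: "We will develop 60 random sequences separately for each center". It does not say outright that the five sequences are generated together.
- **Section XVI (Data Analysis), Primary Analysis.** Both primary outcomes use mixed logistic regression with a fixed effect for assignment, a random slope for centre, and "a random slope to allow for secular trends". The unit over which that slope varies is not given.
- **Section XVI, statistical approach paragraph.** The same models are described with a random centre effect plus unspecified terms for time and for the intervention.

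Neither description names a calendar-week effect or a site-week effect.

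**The concern.** A factor used to restrict the randomisation should normally appear in the analysis. A slope, read literally, follows a steady drift on the logit scale. It cannot follow rises and falls in vaccine attitudes that reach all five EDs in the same week, such as those after a news event or a new variant. If such swings exist and the model omits them, the standard error of the arm contrast may not match its true variability. Both primary tests, acceptance and uptake, use this model, so both would be affected. How much depends on whether the 3:2 rule is enforced every week, which section V leaves slightly open.

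**Working it through.** **1. The plan's own figure.** Section XVIII (Sample Size Considerations) gives control 15%, a 7-point rise to 22%, "at an alpha=0.05 level and a power of at least 0.9", and 645 per arm. With two-sided alpha (sidedness is not stated) and pooled variance, mean p = 0.185:

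n = [1.960·√(2 × 0.185 × 0.815) + 1.2816·√(0.15 × 0.85 + 0.22 × 0.78)]² / 0.07² = (1.0763 + 0.7009)² / 0.0049 = 644.6, so 645 per arm and 1,290 in total. The figure reproduces.

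**2. Size of a site-week.** 5 sites × 50 weeks = 250 site-weeks, and 1,290 / 250 = 5.16 patients each (m).

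**3. How much of a shared swing survives the 3:2 split.** Let s_w be the SD of the shared week effect (assumed) and s_e² = 1/(0.185 × 0.815) = 6.632. In a linear approximation with week omitted,

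true variance / model variance = (s_e² + k·s_w²) / (s_e² + s_w²),

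where k is the mean squared weekly difference in patient numbers between arms, divided by the 5m patients in that week.

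- *Joint list, equal site-weeks.* The arms differ by one site, so k = m²/5m = 0.2m = 1.03. At s_w = 0.5 the ratio is (6.632 + 0.258)/(6.632 + 0.25) = 1.001.
- *Joint list, Poisson site-weeks.* k = (m² + 5m)/5m = 2.03. At s_w = 0.5 the ratio is 7.140/6.882 = 1.037, an SE ratio of 1.019.
- *Separate lists without the rule, Poisson site-weeks.* k = (5m² + 5m)/5m = 6.16. At s_w = 0.5 the ratio is 8.172/6.882 = 1.187, an SE ratio of 1.090. The implied type I error is 2·[1 − Φ(1.96/1.090)] = 7.2%. At s_w = 0.3 the ratio is 7.186/6.722 = 1.069, giving 5.8%.

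With separate lists, a 3:2 or 2:3 split would arise by chance in (10 + 10)/32 = 62.5% of weeks.

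**4. Simulation, joint 3:2 list.** 3,000 trials per setting; each site 25/25; Poisson mean 5.16; site effects and linear time slopes by site. Models were fitted with and without a shared week intercept whose SD was fixed near the simulated value.

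| Week SD (logit) | Type I error: slope only / plus week | True SE ÷ model SE: slope only / plus week | Power: slope only / plus week |
|---|---|---|---|
| 0 | 5.0% / 5.0% | 0.99 / 0.99 | 89.7% / 89.7% |
| 0.25 | 4.9% / 4.4% | 1.01 / 1.00 | 89.4% / 89.1% |
| 0.5 | 5.7% / 5.2% | 1.04 / 1.01 | 87.7% / 87.5% |
| 0.8 | 6.7% / 4.8% | 1.06 / 0.99 | 86.1% / 87.6% |

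Monte Carlo error on type I error is about √(0.05 × 0.95/3,000) = 0.4 points. With very unequal site enrolment, slope-only type I error was 5.4% at SD 0.25 and 6.5% at SD 0.5, against 5.1% and 4.6% with week added. A separate set of runs on the joint list gave slope-only values of 4.7 to 5.1% at SD 0.3 to 0.5, and 6.1% with very unequal sites.

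**5. Simulation, separate lists (permuted pairs within centre, no 3:2 rule).** At SD 0.5, three sets of runs gave slope-only type I error of 6.8%, 7.7% and 7.8%; with week added these became 4.7%, 5.8% and 5.7%. In the first set the mean model SE was 0.153 against a true SD of 0.168, a ratio of 1.10, close to the 1.09 in step 3. At SD 0.3, two sets gave 5.7% and 6.6%, against 4.9% and 5.8% with week added.

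**The case against.** **The time term may already cover this.** The statistical approach paragraph leaves the form of time open, and the Primary Analysis also uses the word slope for the centre term, which the later paragraph calls a random effect. The secular-trend slope could therefore be a loosely worded random time effect. This stands: the fault is an incomplete and inconsistent specification, not a proven omission.

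**The design already does the work.** On the stated 3:2 list, week adds almost nothing to precision (true SE 0.1609 without it and 0.1606 with it at SD 0.5). This stands too. A reader might infer that the trial's standard errors are wrong or that the benefit of stratification is lost. The documents do not support that for the design they describe.

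**The larger figures belong to other designs.** Type I error of 7 to 8% needs lists that break a rule section V states. That section also describes a single study calendar, and section XVIII speaks of a Latin square to avoid period effects, so joint generation is the more natural reading. A reader might also infer a loss of power. Simulation does show 82 to 84% against 88% at SD 0.5, but only with a site-week random intercept and no shared week term. The plan contains no site-week term.

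**The assumed swings are large.** An SD of 0.5 logit around 15% means weekly rates from about 6% to 32% (± 2 SD), moving together in four cities. The plan itself expects gradual change. This is why the conclusion is given as a range. It does not remove the mismatch between randomisation and analysis.

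**Conclusion.** The point holds as a gap in specification with small consequences. Calendar week is a stratum, and neither model description names an effect for it. With the joint 3:2 list and about 5 patients per site-week, type I error is close to 5% for an assumed week SD up to 0.3 logit. It is about 6 to 7% only with large swings (SD 0.8) or very unequal enrolment (SD 0.5). The change in power is at most about 1.5 points over the range tried. Separate lists without the 3:2 rule would give about 7 to 8% at SD 0.5 and 5 to 7% at SD 0.3.

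These figures rest on an assumed week SD, on planned enrolment, and on week variances fixed near the simulated values rather than estimated. A shared week effect is also no substitute for a term for the randomised unit. With a site-week SD of 0.5 and no shared swing, type I error was 6.4% without a week term and 6.3% with one.

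**What to change.** 1. In section XVI, define the time term once, in the same words, in the Primary Analysis and the statistical approach paragraph. Add calendar study week as a random intercept shared by the five centres and crossed with centre. It should sit beside the time trend, not replace it: the models checked above kept the trend. It should also be additional to any site-week term.
2. In section V, state that the five centres' sequences are generated jointly, so that the 3:2 or 2:3 split holds in every week.

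The cost is one sentence in each section, with the two model descriptions aligned, and one variance parameter per model. Study date is already recorded for every patient approached (section XV, Data Recording and Entry), so no new data or patients are needed. With no week variation, the simulated type I error (5.0%) and power (89.7%) were unchanged by the extra term.

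### The plan means to act on differences in effect between subgroups, but specifies no test of whether the effects differ

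*Combined protocol and SAP*

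**What the plan says.** Under Data Analysis, the Sub-analyses section contains three plans. For the ED Usual Source of Care (USCARE) group: "We will conduct subgroup analyses of the same primary outcomes of this ED Usual Source of Care group". For site and demographic factors: "We will additionally stratify outcomes by study site (representing different regions of the country and different communities), age, gender, and race/ethnicity". For patient experience, with the list left open: "We will also analyze outcomes according to patient-level experience characteristics, such as having already had COVID-19".

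The Statistical approach text in the same chapter adds that the effect will be examined on "acceptance in patient sub-groups, especially African Americans and Latinos", and gives the purpose: "PROCOVAXED may work for one patient sub-group and not others - these additional analyses will guide future directions and modifications of PROCOVAXED messaging".

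On the model, that text lists a random center effect "as well as terms for time and intervention", and directs the hypothesis tests at the significance of the intervention indicator. The Primary Analysis section pairs the treatment test with 95% confidence intervals. Neither text includes a subgroup-by-intervention term. No section gives a test of whether effects differ between subgroups, subgroup power, multiplicity control, or a statement that subgroup findings are exploratory.

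**The concern.** Saying that an intervention works in one group and not in another is a statement about a difference between two effects. A within-stratum test of the intervention coefficient answers another question: whether the effect in that stratum can be told apart from zero. With limited power in each stratum, some strata will reach significance and others will not even when the true effect is identical in all of them. Unequal stratum sizes make two-group patterns more frequent, but equal strata produce them too.

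At stake are the subgroup conclusions and the later changes to messaging that they are meant to inform, including by race and ethnicity. The two primary tests are not affected.

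**Working it through.** **Inputs.** From Sample Size Considerations: control rate 15%, improvement 7 points (so 22%), alpha 0.05, power at least 0.9, 645 per arm, formula for individual randomization. From Randomization: five sites. The documents do not give subgroup shares, so every split below is an assumption.

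**The plan's own figure.** Two-sided test, pooled variance under the null, no continuity correction, mean rate 0.185:

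n per arm = [1.960 × √(2 × 0.185 × 0.815) + 1.282 × √(0.15 × 0.85 + 0.22 × 0.78)]² / 0.07²
= (1.960 × 0.5491 + 1.282 × 0.5469)² / 0.0049 = 644.6, rounded up to 645.

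This reproduces the stated 1,290. The plan does not say whether alpha is two-sided; a one-sided calculation gives 526 per arm and does not match.

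**Power within a stratum.** With n per arm in the stratum and the same true effect:

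power = Φ[(0.07 × √n − 1.960 × 0.5491) / 0.5469]

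| Stratum | n per arm | Power |
|---|---|---|
| Whole trial | 645 | 0.900 |
| Three quarters | 483.75 | 0.802 |
| One half | 322.5 | 0.630 |
| One quarter | 161.25 | 0.366 |
| One of five equal sites | 129 | 0.304 |

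**Chance of a mixed pattern when the effect is uniform.** Taking strata as independent, P(at least one significant and at least one not) = 1 − Π(power) − Π(1 − power).

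- 50:50 split: 2 × 0.630 × 0.370 = 0.47.
- 25:75 split: 0.366 × 0.198 + 0.802 × 0.634 = 0.58.
- Five equal sites: 1 − 0.304⁵ − 0.696⁵ = 1 − 0.003 − 0.164 = 0.83.

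The other two-group splits tried gave 0.49 (60:40), 0.54 (70:30), 0.63 (80:20) and 0.74 (90:10). Four groups at assumed shares of 40/30/20/10 gave 0.83. A simulation of 200,000 trials gave 0.47 for two equal strata, 0.54 for 70:30 and 0.83 for five sites.

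**Interaction test under the same uniform effect.** In that simulation, a heterogeneity test on the log odds ratio rejected in 4.9% of trials (two equal strata), 4.8% (70:30) and 4.3% (five sites). This is per factor and per outcome, with a 15% baseline in every stratum.

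**Power of the interaction test, two equal halves.** The standard error of the effect in one half is √[(0.1275 + 0.1716)/322.5] = 0.0305. For the difference between halves it is 0.0305 × √2 = 0.0431. Power for a 7-point difference in effect is Φ(0.07/0.0431 − 1.96) = 0.37. For a 14-point difference it is 0.90.

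**Sensitivity to clustering.** The documents give no intracluster correlation. Dividing n by an assumed design effect of 1.5 or 2 gives a mixed pattern in 50% or 46% of trials for equal halves, 56% or 51% for 25:75, and 71% or 61% for five sites.

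**The case against.** The strongest reply is that the plan is silent here, not wrong. A reader might infer that subgroups will be judged by setting a significant p-value beside a non-significant one. The documents state no such rule. They speak of stratifying outcomes and examining effects, they do not exclude an interaction, and the focus on the intervention indicator is written for the Aim III and IV models before subgroups come up. Likewise, "PROCOVAXED may work for one patient sub-group and not others" explains why the investigators will look; it does not commit them to that conclusion. All of this stands. What remains is that the plan states a between-group question and a use for the answer, and names no method able to answer it.

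Other replies stand in part:

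- **USCARE.** This is planned as an analysis within one group, and USCARE patients are named in Aim IV. No contrast with other patients is stated, so it needs no interaction as it is.
- **Site.** The Primary Analysis section mentions a random slope for clustering by center. Read literally, as a slope on intervention, it would already let the effect vary by site. The Statistical approach text has only a random center effect, so the point is unclear.
- **The 5% rate.** It does not cover the whole set of tests. Five independent factors give 1 − 0.95⁵ = 23% for one outcome, and ten independent tests over two outcomes give 1 − 0.95¹⁰ = 40%. It also depends on equal baselines: a uniform 7-point gain is an odds ratio of 1.84 from 10% to 17%, but 1.37 from 30% to 37%. A logistic interaction could then be present with no difference on the risk scale.
- **Consequence.** A reader might infer that subgroup results would change the messaging during the trial. The reviews at months 4 and 8 rest on subject feedback, and matching messengers to patients already follows from the Aim I interviews. The use stated for subgroup results is "these additional analyses will guide future directions and modifications of PROCOVAXED messaging".

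**Conclusion.** The point holds as a gap in method for the secondary analyses. The plan wants to learn whether the messaging works better in some groups than in others, intends to use the answer, and specifies no test of that difference. If stratified results were read one stratum at a time, a uniform effect would look uneven in about 47% of trials for two equal halves, 58% for a 25:75 split, and 83% for five equal sites.

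The figures rest on the plan's planning rates, a two-sided 0.05 test in each stratum, equal baselines, assumed shares and no clustering. The assumed design effects change the numbers but not the conclusion. The documents do not support the stronger reading that a comparison of p-values is the plan's stated decision rule. The change should be made before the data are examined.

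**What to change.** For site, age, gender, race/ethnicity and prior COVID-19, add the subgroup and its interaction with intervention to the primary mixed logistic model. For site, use either a site-by-intervention term or a random intervention slope by site, whichever is consistent with the center effect already in the model.

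Report the interaction estimate and the within-group effects, each with a 95% confidence interval, on both the odds-ratio and the risk-difference scale, since baselines may differ between groups. Base any claim of differential effect on the interaction and not on separate within-group p-values. Label these analyses exploratory and say that multiplicity is not controlled. The USCARE analysis can stand as planned; it needs an interaction only if its effect is to be contrasted with that in other patients.

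The cost is SAP wording and one interaction analysis per factor and outcome, with no new data or enrollment. The drawback is low power (about 37% for a 7-point difference between equal halves), so most subgroup differences will be reported as inconclusive.
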